7.3.2. Subgroup Analyses for Primary Endpoint

Subgroups will be formed based on the following participant characteristics and baseline variables for those participants whose data are available:

- Sex: female versus male
- Baseline categorical age: ≥ 18 and < 65 versus ≥ 65
- Baseline duration of disease: ≤ 1 , > 1 and ≤ 5 , > 5
- Race: Black/African American versus White/Asian/other

The primary efficacy endpoint will be summarized using descriptive statistics based on the ITT population for the aforementioned subgroups.

7.4. Analysis of the Secondary Efficacy Parameters

All secondary efficacy analyses will be conducted for the ITT population.

7.4.1. Continuous Efficacy Endpoints

Summary statistics for the following continuous measurements, including change from baseline, will be presented for each treatment arm:

- By-visit Skin Pain NRS score

The summary statistics, including sample size, mean, median, standard deviation, minimum, maximum, first quartile, third quartile, and 95% CI, will be presented by visit.

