2. INTRODUCTION

2.1. Background

Lichen planus is an inflammatory skin condition characterized by purple, polygonal, pruritic papules, and plaques. The lesions are often covered by lacy, reticular, white lines known as Wickham striae. Lichen planus can affect any ectodermally derived tissues, including the skin (most commonly), nails, and mucous membranes. Onset is usually acute, affecting the flexor surfaces of the wrists, forearms, and legs. Oral LP can be the sole clinical presentation of the disease or accompanied by cutaneous or other mucosal manifestations, including the genital area, gastrointestinal tract, and eyes. Classic cases of LP may be diagnosed clinically, but a biopsy is often helpful and is required for more atypical cases ([Usatine and Tinitigan 2011](#)). Itch is present in most patients and is considered the most bothersome symptoms of LP ([Welz-Kubiak and Reich 2013](#)). Lichen planus is associated with relatively high rates of depression and anxiety. A recent meta-analysis showed a high prevalence of signs of depression (27%) and anxiety (28%) in patients with LP ([Jalenques et al 2020](#)).

The prevalence of LP is 0.89% in the general population and 0.98% in patients seeking dermatological care, according to a recent meta-analysis of 46 studies ([Li et al 2020](#)). The prevalence of cutaneous LP is reported to range between 0.2% and 1.0% of the adult population, and it is outnumbered by oral LP in most study populations ([Boyd and Neldner 1991](#), [Le Cleach and Chosidow 2012](#)). Patients with LP are usually between the ages of 30 and 60 years, and there appears to be a slightly higher prevalence in women (60%; [Axell and Rundquist 1987](#)). While oral LP affects females more frequently than males ([Axell and Rundquist 1987](#), [Li et al 2020](#)), cutaneous LP does not demonstrate a prominent sex predilection ([Irvine et al 1991](#)). Cutaneous LP tends to manifest during the fifth and sixth decades of life, with almost two-thirds of patients presenting with the disease between the ages of 30 and 60 years ([Schwager et al 2019](#), [Wagner et al 2013](#)). The majority of cutaneous LP lesions resolve spontaneously over 1 to 2 years, often with a residual hyperpigmented macule ([Weston and Payette 2015](#)).

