2.1.1. Scientific Rationale for Study Design

Similar to AD and vitiligo, LP is considered to be an inflammatory dermatosis. The pathogenesis of LP involves autoimmunity and several cytokines that are dependent on the JAK-STAT pathway for signal transduction. Similar to AD and vitiligo, JAK1- and JAK2-associated cytokines are involved in the pathogenesis of cutaneous LP. Prior studies have shown overexpression of IFN- γ , IL-21, IL-4, IL-12A, and tumor necrosis factor in LP ([Pietschke et al 2021](#), [Shao et al 2019](#)). Ruxolitinib is a selective inhibitor of JAK1 and JAK2, and based on its demonstrated efficacy in both AD and vitiligo in well-designed pivotal Phase 3 trials (INCB 18424-303/-304 and INCB 18424-306/-307) and data from [Mangold et al \(2021\)](#), ruxolitinib 1.5% cream is expected to have potential activity in cutaneous LP.

While the study by [Mangold et al \(2021\)](#) provides preliminary evidence of the efficacy of ruxolitinib 1.5% cream in patients with LP, this was a single-arm study with a small sample size, and these findings need to be replicated in a larger randomized controlled trial as a proof of concept. Lichen planus lesions mostly resolve spontaneously over a period of 1 to 2 years, and the aim of treatment is to hasten recovery and reduce associated symptoms such as itching. Given the high rate of spontaneous resolution, it is important to demonstrate the efficacy of ruxolitinib 1.5% cream against a VC arm. Although ruxolitinib 1.5% cream has been demonstrated to improve AD at 8 weeks, LP lesions involve significantly more skin changes. [Mangold et al \(2021\)](#) demonstrated reduction in lesion count by 50% after 4 weeks of open-label treatment with ruxolitinib 1.5% cream. However, concern with spontaneous resolution of LP remains. In the study by [Mangold et al \(2021\)](#), approximately 33% of control lesions achieved treatment response, as defined by $\geq 50\%$ reduction in mCAILS score at Week 4. Based on these findings, it is crucial to demonstrate the efficacy of ruxolitinib 1.5% cream in participants with cutaneous LP as a proof-of-concept Phase 2 study with a longer treatment period (16 weeks was chosen for this study) before moving to confirmatory Phase 3 studies. In addition, there is a need to demonstrate the long-term safety and efficacy of ruxolitinib 1.5% cream in LP by including an OLE period.

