10.4.2. Secondary Analysis

All secondary [REDACTED] efficacy variables will be summarized using descriptive statistics based on the ITT population. For categorical measurements, summary statistics will include sample size, frequency, and percentages. For continuous measurements, summary statistics will include sample size, mean, median, STD, standard error of the mean, minimum, and maximum. Summary statistics for continuous measures will be provided for baseline, the actual measurements at each visit, and the change and percentage change from baseline at each visit, if applicable. The Itch NRS score as well as the Skin Pain NRS score for each visit will be determined by averaging the 7 daily scores for Itch or Skin Pain before the corresponding visit day. If 4 or more daily scores are missing (out of the 7), the Itch NRS or Skin Pain NRS score at the visit will be set to missing.

For the time to achieve ITCH4, a log-rank test stratified by randomization stratification factor will be used for between-treatment group comparisons. The hazard ratio and its 95% CI will be estimated based on the stratified Cox regression model using Efron's method accounting for ties. Kaplan-Meier curves will be presented by treatment groups. The number of participants, number of events, and number of censorings will be summarized by treatment groups. The Kaplan-Meier estimate of median time will be presented with its 95% CI. The 95% CI will be calculated using the method by Brookmeyer and Crowley (1982).

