2.2. Study Objectives and Endpoints

[Table 1](#) presents the objectives and endpoints.

Table 1: Objectives and Endpoints

Objectives	Endpoints
Primary	
To establish the efficacy of ruxolitinib 1.5% cream BID in participants with cutaneous LP.	
IGA-TS response is defined as an IGA score of 0 or 1 with \geq 2-grade improvement from baseline at Week 16; this is the proportion of participants achieving IGA-TS at Week 16.
Secondary	
To further assess the treatment effects of ruxolitinib 1.5% cream BID in participants with cutaneous LP.	
IGA-TS response at each scheduled postbaseline visit up to and including Week 32 will be the proportion of participants achieving IGA-TS at each scheduled postbaseline visit.ITCH4 response is defined as a \geq 4-point improvement in Itch NRS score from baseline at each scheduled postbaseline visit, up to and including Week 32; it is the proportion of participants with ITCH4 at each scheduled postbaseline visit.Time to achieve ITCH4.Change from baseline in the Skin Pain NRS score at each scheduled postbaseline visit, up to and including Week 32.
To evaluate the safety and tolerability of ruxolitinib 1.5% cream BID.	
The type, frequency, and severity of AEs, including changes in vital signs and clinical laboratory blood samples.

Table 1: Objectives and Endpoints (Continued)

Objectives	Endpoints
[REDACTED]	

Table 1: Objectives and Endpoints (Continued)

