7.2.6.2. Skin Pain Numerical Rating Scale

Participants will be instructed to complete and record the Skin Pain NRS in a diary each evening beginning on the day of screening through Week 32 or treatment discontinuation. Participants will rate their pain, which will include all types of pain (eg, burning, tearing, pulling, stabbing, etc) severity of the LP by selecting a number from 0 (no pain) to 10 (worst imaginable pain) that best describes the worst level of pain they experienced in the past 24 hours.

The participant's baseline Skin Pain NRS score will be determined by averaging the 7 daily NRS scores before Day 1 (ie, Days -7 to -1). The by-visit Skin Pain NRS score for postbaseline visits will be determined by averaging the 7 daily NRS scores before the visit day. If 4 or more daily scores (out of the 7) are missing, the Skin Pain NRS score at the visit will be set to missing. No imputation will be performed for missing values.

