7.4.2. Categorical Efficacy Endpoints

For the following categorical parameters, summary statistics, including sample size, frequency, and percentages, will be presented by visit.

[figure not shown]
- IGA-TS response
- By-visit ITCH4 response

[figure not shown]
In addition, a Cochran-Mantel-Haenszel test stratified by baseline IGA score (3 or 4) at a 2-sided $\alpha = 0.05$ level will be used for the comparison between ruxolitinib 1.5% cream BID and vehicle cream BID at Week 16 for ITCH4 response. The p-value and stratum-adjusted response rate difference with 95% CI will be provided.

[figure not shown]

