7.4.3. Time-To-Event Efficacy Endpoint

The time to achieve Itch NRS score improvement of at least 4 points from baseline (ie, ITCH4) will use the daily Itch NRS score in comparison to baseline Itch NRS score in the DBVC period. A log-rank test stratified by randomization stratification factor, baseline IGA score (3 or 4), will be used for between-treatment group comparisons. The hazard ratio and its 95% CI will be estimated based on the stratified Cox regression model using Efron's method accounting for ties. Kaplan-Meier curves will be presented by treatment groups. The number of participants, number of participants with events, and number of participants censored will be summarized by treatment group. The Kaplan-Meier estimate of median time will be presented with its 95% CI. The 95% CI will be calculated using the method by Brookmeyer and Crowley (1982).

The last available value for time to ITCH4 during the DBVC period is the last nonmissing measurement obtained after the first application of study cream and within 30 days after the last application of study cream in DBVC period, or before the first application of study cream in the OLE period, whichever is earlier.

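### Skin Pain NRS change, a secondary endpoint under the treatment-effects objective, has no between-arm estimate with a confidence interval in the readable SAP 7.4.1

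*SAP*

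**What the plan says.** SAP 2.2 (Table 1) lists change from baseline in Skin Pain NRS, at each visit to Week 32, as a secondary endpoint. The objective it serves is: "To further assess the treatment effects of ruxolitinib 1.5% cream BID in participants with cutaneous LP".

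SAP 7.4.1 gives the analysis: "Summary statistics for the following continuous measurements, including change from baseline, will be presented for each treatment arm". Skin Pain is the only measure in the readable list. The statistics are n, mean, median, SD, range, quartiles and a 95% CI, by visit. SAP 7.2.6.2 adds: "No imputation will be performed for missing values".

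The two itch endpoints under the same objective are treated differently:

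- **ITCH4 at Week 16** (SAP 7.4.2) has a Cochran-Mantel-Haenszel test stratified by baseline IGA, and "The p-value and stratum-adjusted response rate difference with 95% CI will be provided".
- **Time to ITCH4** (SAP 7.4.3) has a stratified log-rank test, and "The hazard ratio and its 95% CI will be estimated based on the stratified Cox regression model".

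Protocol 10.4.2 sets the general rule that secondary "efficacy variables will be summarized using descriptive statistics based on the ITT population". It names a between-group method only for time to ITCH4.

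**The concern.** In a vehicle-controlled trial a treatment effect is a contrast between arms, and the pain endpoint has no planned contrast. The 95% CI in SAP 7.4.1 does not supply one, because it belongs to the statistics given for each arm.

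Readers would have to set two per-arm means side by side or work out a crude difference. Judging by whether the two per-arm intervals overlap is a poor substitute. With 30 per arm and an assumed SD of change of 2.5 points, each per-arm half-width is 0.93, so the intervals separate only when the means differ by about 1.87. The half-width for the difference itself is 1.29.

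The baseline pain score and the IGA stratum are already collected and could sharpen the estimate. If a contrast is added later, its form would be chosen after the sponsor is unblinded at the primary database lock (SAP 10).

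**Working it through.** **The plan's own figures.** The documents give no figure for Skin Pain. The one sizing statement (Protocol 10.1: 58% vs 20%, Fisher exact test, 2-sided 0.05, over 80% power) reproduces. Exact power with 30 per arm is 81.0%. It does not bear on pain.

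**Inputs.** From the documents: about 60 participants randomized 1:1, so n = 30 per arm. Assumed, because the documents do not give them: SD of the pain score 2.5 points at both baseline and Week 16, correlation r between them of 0.3, 0.5 or 0.7, and complete data.

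**Formulas for the 95% CI half-width at Week 16**

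- Crude difference in change: t(2n−2) × SD × √[2(1−r)] × √(2/n)
- Difference adjusted for baseline pain: t(2n−3) × SD × √(1−r²) × √(2/n) × √[1 + 1/(2n−4)]. The last term is the small-sample cost of estimating the slope, √(1 + 1/56) = 1.009.
- Large-sample variance ratio, adjusted to crude: (1−r²)/[2(1−r)] = (1+r)/2

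Example at r = 0.5:

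- Crude: 2.002 × 2.5 × 1 × 0.2582 = 1.29
- Adjusted: 2.002 × 2.5 × 0.8660 × 0.2582 × 1.009 = 1.13

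| r | Variance ratio | Crude half-width | Adjusted half-width | Narrower by | n per arm for crude to match (30/ratio) |
|---|---|---|---|---|---|
| 0.3 | 0.65 | 1.53 | 1.24 | 19% | 46.2 |
| 0.5 | 0.75 | 1.29 | 1.13 | 13% | 40.0 |
| 0.7 | 0.85 | 1.00 | 0.93 | 7% | 35.3 |

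Half-widths scale in proportion to the assumed SD. The IGA stratum term costs one more degree of freedom, which is negligible here, and any gain from it is not counted.

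**Assumed 20% loss (24 per arm).** The factor becomes √(1 + 1/44) = 1.011. The half-width goes from 1.72 to 1.40, 1.45 to 1.27 and 1.13 to 1.05.

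**Unequal SDs.** With k = SD at Week 16 / SD at baseline, the ratio is k²(1−r²)/(1 + k² − 2rk).

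- k = 0.8: 0.50, 0.57, 0.63
- k = 1.2: 0.76, 0.87, 0.97

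**Scores bounded at 0 and 10.** This was simulated with 20,000 trials per setting, latent SD 2.5, vehicle change −1, a 1-point latent treatment effect, and latent baseline mean 1 to 5. The variance ratio runs from 0.42 to 0.83. The 1-point latent effect shows up as only 0.42 to 0.92 points under both estimators, so adjustment gains precision but does not undo a floor effect.

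**Overall range.** Ratios of 0.42 to 0.97 give 30/0.42 = 71.4 to 30/0.97 = 30.9 per arm. That is roughly 1 to 41 extra participants per arm.

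**The case against.** The strongest reply is that the sponsor meant pain to be descriptive. SAP 7.4.1 does what Protocol 10.4.2 says. Alpha is assigned only to the primary endpoint (SAP 3.2). The protocol's rationale is about itch: "Itch is present in most patients and is considered the most bothersome symptoms of LP", and "the aim of treatment is to hasten recovery and reduce associated symptoms such as itching". Entry requires a minimum itch score (Protocol 5.1, criterion 6) but no minimum pain score. ITCH4 and IGA-TS at visits other than Week 16 are descriptive too. All of this stands, and it is why the point is a suggestion. It does not bar the addition, because SAP 7.4.2 already goes beyond the protocol's descriptive default for ITCH4 at Week 16.

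A second reply is that a plain prespecified difference would fill the gap, and that neither itch analysis adjusts for baseline itch. Also true. The figures above measure the further gain from using the baseline score. With no missing data, a determined reader could even back out the baseline covariance from the SDs of baseline, Week 16 and change. That fails once Week 16 values are missing, because the baseline SD then covers different participants. It never supplies the stratum term.

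A third reply is that low baseline pain would strain a normal-theory model. This stands as a limit on interpretation.

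Stronger inferences that the documents do not support:

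- **That the SAP contradicts the protocol.** It does not.
- **That there is a false-positive risk.** No test of pain is planned.
- **That the loss is 5 to 16 participants per arm.** That range holds only with equal SDs and unbounded scores.
- **That a full repeated-measures model is needed.** One Week 16 contrast is enough.
- **That no pain contrast exists anywhere in the SAP.** Text after 7.4.3 and several efficacy tables are redacted or not shown, although 7.4.1 reads as complete.

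**Conclusion.** The point holds as a low-severity improvement. In the readable SAP 7.4.1, a secondary endpoint under the treatment-effects objective has only per-arm observed-case summaries, while the two itch endpoints have between-arm estimates with confidence intervals. Under equal SDs and complete data, a baseline-adjusted interval would be 19%, 13% or 7% narrower than a crude one at r = 0.3, 0.5 or 0.7. Across the wider assumptions the variance ratio runs from about 0.42 to 0.97. The documents give no pain SD, correlation or dropout rate, so the true gain is unknown and could be close to nothing. The primary analysis and its error rate are not affected.

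**What to change.** Add to SAP 7.4.1, for the double-blind period only, since vehicle participants cross over to active cream after Week 16:

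> The between-arm difference in Skin Pain NRS change from baseline at Week 16 will be estimated from a linear model (ANCOVA) with treatment, baseline Skin Pain NRS and baseline IGA stratum, and reported with a nominal 95% CI that is not controlled for multiplicity.

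A repeated-measures model is optional. If one is used, its covariance structure and a fallback should be named in advance.

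State the limits beside it. The observed-case estimate assumes Week 16 values are missing at random given the model terms. It does not remove a floor effect. It also does not remove bias from discontinuation, for example when the area to be treated exceeds 20% BSA (Protocol 7.1.1), because the pain diary ends when treatment is discontinued (SAP 7.2.6.2).

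Keep the descriptive tables, including those for the open-label period, and record the addition in SAP 11.1. If the sponsor prefers to leave pain descriptive, one sentence saying so would settle the matter.

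The cost is one SAP paragraph, one table shell and one model run on data already collected. The primary test and alpha are unchanged. The downside is one more nominal estimate, resting on a missing-data assumption that the data cannot check.

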7.4.2. Categorical Efficacy Endpoints

For the following categorical parameters, summary statistics, including sample size, frequency, and percentages, will be presented by visit.

[figure not shown]
- IGA-TS response
- By-visit ITCH4 response

[figure not shown]
In addition, a Cochran-Mantel-Haenszel test stratified by baseline IGA score (3 or 4) at a 2-sided $\alpha = 0.05$ level will be used for the comparison between ruxolitinib 1.5% cream BID and vehicle cream BID at Week 16 for ITCH4 response. The p-value and stratum-adjusted response rate difference with 95% CI will be provided.

[figure not shown]
7.4.3. Time-To-Event Efficacy Endpoint

The time to achieve Itch NRS score improvement of at least 4 points from baseline (ie, ITCH4) will use the daily Itch NRS score in comparison to baseline Itch NRS score in the DBVC period. A log-rank test stratified by randomization stratification factor, baseline IGA score (3 or 4), will be used for between-treatment group comparisons. The hazard ratio and its 95% CI will be estimated based on the stratified Cox regression model using Efron's method accounting for ties. Kaplan-Meier curves will be presented by treatment groups. The number of participants, number of participants with events, and number of participants censored will be summarized by treatment group. The Kaplan-Meier estimate of median time will be presented with its 95% CI. The 95% CI will be calculated using the method by Brookmeyer and Crowley (1982).

The last available value for time to ITCH4 during the DBVC period is the last nonmissing measurement obtained after the first application of study cream and within 30 days after the last application of study cream in DBVC period, or before the first application of study cream in the OLE period, whichever is earlier.

